
mini-vaccination stations in communities highly impacted by the pandemic and identifying individual and structural barriers to COVID-19 immunization (Phase 2). Specific aims include:

Aim 1. To evaluate the preliminary impact of 2VIDA! compared to the standard-of-care for COVID-19 vaccination services among Latinx and AA adults ≥ 16 years (N=1000) in San Diego. We will use a 2-armed randomized controlled trial (RCT)* where Latinx and AA adults ≥ 16 years or older from six participating community health centers (CHC) and surrounding communities will be assigned to the 2VIDA! intervention (n=3 CHC; N=500 participants) or to the control site (e.g., standard of care) (n=3 CHC; N=500 participants). Data will be collected on a) sociodemographic characteristics; b) characteristics associated with social marginalization; c) access to and utilization of health care; d) vaccination history, interest, hesitancy and uptake; e) perceptions of the COVID-19 vaccine (e.g., fears, myths, etc.); f) general health; and h) trust in government, research, and social agencies, i) satisfaction with 2VIDA!; at baseline and 4-week follow-up. We hypothesize that at follow-up, compared to control participants, 2VIDA! participants will:

H.1. have increased knowledge about the COVID-19 vaccine (including medically accurate information, benefits, and risks);
H.2. more likely to receive the COVID-19 vaccine;
H.3. more likely to complete vaccine series (based on Centers for Disease Control and Prevention [CDC] recommendations).¹

Aim 2. To assess feasibility, acceptability, and intervention effects of 2VIDA! To assess feasibility and acceptability, we will utilize quantitative methods to track recruitment, condition assignment, participant retention, intervention implementation, and potential threats (e.g., contamination). We will also utilize qualitative methods to assess acceptability via focus groups with participants to understand potential for broad implementation (e.g., what components did they receive of the intervention, client satisfaction, linkage to COVID-19 services). To assess intervention effects, we will examine participant vaccination rates/completion across both groups.

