*Please note that only one community health center out of their 25 clinics is currently delivering 2VIDA! as a clinical program and all of their clinics are offering the vaccine on site (no mini-vaccination stations). For the purposes of this research, we will randomize 6 community health centers and their surrounding communities that are predominantly Latinx and AA to receive either 2VIDA! or the standard of care for vaccine delivery (i.e. no components of 2VIDA! will be deployed). In order to avoid contamination, the community health center where the 2VIDA! was developed (i.e., Chula Vista) and is currently being implemented as a clinical program will be excluded from this study. Additionally, SYH is currently offering the vaccine at their community health centers, however, there is low vaccine uptake, therefore we believe this study will help increase interest in the vaccine and address vaccine hesitancy by working with the community.

6. BACKGROUND AND SIGNIFICANCE (2-3 paragraphs maximum)

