10. RECRUITMENT

Six SYHealth community health centers across San Diego County have been selected based on their serving predominantly Latinx and AA client population and having the Zip codes with the highest number of COVID-19 cases in the County. These clinics are located in National City, Logan Heights, Lincoln Park, Valencia Park and San Ysidro. Each clinic will be randomly selected and randomized evenly to either the intervention or control conditions, using computer-generated randomization plans prepared using SAS statistical software under the direction of the lead study statistician. Clinic-level randomization was selected to minimize between-arm contamination of intervention and control conditions. Participants from both intervention (n=500) and control sites (n=500) will be recruited using reactive recruitment, including the use of community partner social media platforms, and flyers distributed in the SYH target health centers and high traffic, readily visible areas, where eligible participants are likely to see them (e.g., grocery stores, local CBO's, parks, barber shop, cafés, food banks, gyms, local restaurants). Flyers will include study information and contact information for study staff. Likewise, the project staff publicized the rapid vaccine effort (e.g., mini-vaccination stations) by posting flyers that noted locations, dates, and times of vaccine distribution, and through presentations about the project at community meetings. Project staffing, training, and support, including the selection of nurses and outreach staff (e.g., peer-health educators and research assistants) with complementary research skills and personal knowledge of the community will be key to the success of the project. Two bilingual Latinx (one male and one female) and two AA (one male and one female) outreach workers trained in research ethics and protocols, and familiar with this population will approach individuals who appear to be eligible (Latinx and AA adults ages 16 years or older) at the SYH community centers and mini-vaccination stations in the participating communities, confirm eligibility, and describe the study to those eligible. Research staff will update time logs and continuously update our sampling frame until recruitment is finalized. The reason for refusal or ineligibility will be recorded. Extensive efforts will be made to have an equal representation of Latinx and Black community members and at least 40% women.

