Cover Page for ClinicalTrials.gov

Document: Statistical Analysis Plan

Official Study Title: Project 2VIDA! COVID-19 Vaccine Intervention Delivery for Adults in Southern California

NCT number: NCT05022472

Document date: February 5, 2021

STATISTICAL DESIGN AND POWER CALCULATIONS

We will approach overall data analyses using a multivariate repeated measures design (i.e., doubly multivariate) to assess mean differences in treatment and control groups on our primary (acceptance of COVID-19 vaccine and vaccine series completion) and secondary outcome variables (increased knowledge of COVID-19 vaccine, increased access to COVID-19 vaccine, vaccine hesitancy). Additional measures at baseline and follow-up will be used as covariates (e.g., outreach and health communication, vaccine hesitancy or mistrust). Mean differences, both within and between treatment and control groups as well as group by treatment interaction effects will be analyzed. The targeted sample size is sufficient to detect a small effect size (.20) with power = .90 at alpha = .05 accounting for moderate participant attrition. Descriptive Statistics. To describe the overall sample regarding demographics, structural and individual barriers, and potential covariates of intervention effects at baseline, prevalence statistics and means and standard deviation will be provided for all baseline variables; Cronbach's alpha of .70 will be required to be considered reliable. Baseline Analyses to Detect Differences Between Treatment Groups. Chi-square analyses and paired t-tests will be used to detect differences in demographics, knowledge of COVID-19 vaccine, access to COVID-19 vaccine, acceptance of COVID-19 vaccine and series completion, COVID-19 resource-seeking behaviors and linkage into care between intervention and control groups. Demographic variables included in these analyses will be age, gender, race/ethnicity, household income, marital status, and having insurance. Those variables differing across treatment groups at the $p < .20$ level will be included in subsequent adjusted outcome analyses.

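### The stated power of .90 for an effect of .20 ignores that clinics, three per arm, are randomised; a two-sided unadjusted clinic-level test has at most .66

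*SAP*

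**What the plan says.** The only sample-size justification is one sentence, in the SAP under Statistical Design and Power Calculations and in protocol section 8 under Data Analysis. It describes the target sample as "sufficient to detect a small effect size (.20) with power = .90 at alpha = .05 accounting for moderate participant attrition". Attrition is the only allowance named, and no rate is given. Sidedness, the metric of the effect and any baseline correlation are not stated.

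The SAP describes its analysis as one "to assess mean differences in treatment and control groups on our primary (acceptance of COVID-19 vaccine and vaccine series completion" (and on secondary outcomes). Hence .20 is read here as a standardised mean difference.

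The protocol randomises clinics, not people. The note in section 5 says "we will randomize 6 community health centers and their surrounding communities that are predominantly Latinx and AA"; section 10 says "Each clinic will be randomly selected and randomized evenly to either the intervention or control conditions". Aim 1 gives the arms as "n=3 CHC; N=500 participants) or to the control site (e.g., standard of care) (n=3 CHC; N=500 participants". Section 10 explains clinic-level allocation as a guard against contamination. Neither document carries it into the power calculation.

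**The concern.** When clinics are randomised, the treatment effect is judged against variation between clinics. This costs power in two ways. Any similarity among participants of one clinic inflates the variance of the arm means, and with three clinics per arm that variance is estimated on only 4 degrees of freedom. A sample that gives about .90 when individuals are randomised can then give far less.

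A reader who accepts .90 will take a non-significant result as good evidence against a small effect. Protocol section 16 expects a null result to inform later programmes, so the figure bears on how the trial will be read.

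**Working it through.** **Inputs from the documents:** d = .20, alpha = .05, stated power .90 (SAP); 500 participants and 3 clinics per arm (protocol, Aim 1), so m = 500/3 = 166.7 per clinic.

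**Assumptions, because the documents are silent:** two-sided test unless noted, equal clinic sizes, ICC from 0 to .05, attrition 0 to 20%.

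**1. The plan's own figure, participants independent.** ncp = d/√(2/n) = .20/√(2/500) = 3.162. Two-sided power = Φ(3.162 − 1.960) = .885. With attrition: .85 at 10% (450 per arm) and .81 at 20% (400 per arm). Other routes to about .90 are a one-sided test at 10% attrition (.91) or at 15% (.90), and a two-sided test with baseline correlation r = .5 at 20% (.90). So .90 is roughly what individual randomisation would give. At that level it is under-specified rather than shown to be wrong.

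**2. Clinic-level test.** With n participants per arm:

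- DE = 1 + (m − 1) × ICC, with m = n/3
- ncp = d/√(2 × DE × (1 − r²)/n)
- df = 6 − 2 = 4, two-sided critical t = 2.776
- power from the noncentral t distribution

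At ICC 0, DE = 1 and ncp = 3.162, as in step 1, but against 2.776 on 4 df the power is .66. At ICC .01, DE = 1 + 165.7 × .01 = 2.66, ncp = 3.162/√2.66 = 1.94, and power is .32.

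| ICC (assumed) | Power, no attrition | Power, 20% attrition | Effect at .90 power, no attrition | Effect at .90 power, 20% attrition |
|---|---|---|---|---|
| 0 | .66 | .57 | 0.28 SD | 0.31 SD |
| .005 | .43 | .39 | 0.38 SD | 0.40 SD |
| .01 | .32 | .30 | 0.45 SD | 0.47 SD |
| .02 | .22 | .21 | 0.58 SD | 0.59 SD |
| .05 | .13 | .13 | 0.85 SD | 0.86 SD |

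Simulated clinic-level t-tests (200,000 replicates, no attrition) gave .66, .32 and .13 at ICC 0, .01 and .05. Unequal clinics do worse: at ICC 0, sizes of 200/200/100 per arm give .63 and 300/100/100 give .57. The detectable effect reaches twice .20 at an ICC of about .0065, or about .005 with 20% attrition.

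**3. Source of the loss.** At ICC 0 the fall from .885 to .66 comes from the 4 df alone. Above 0 the design effect is enough by itself: with large df, power is .65 at ICC .005, .49 at .01 and .18 at .05.

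**4. More favourable assumptions (4 df).** Adjustment is taken to shrink the variance by 1 − r², with the ICC unchanged. At ICC 0 with no attrition:

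- one-sided: .83
- r = .5, two-sided: .78
- both: .91

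The last falls to .88 at 10% attrition and .85 at 20%. Without attrition it falls to .72 at ICC .005 and .58 at ICC .01. A two-sided test reaches .90 only with r = .69 (ICC 0, no attrition), r = .77 (ICC 0, 20% attrition) or r = .90 (ICC .01, no attrition).

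**5. More participants in the same clinics.** As m grows, ncp tends to d/√(2 × ICC/3). At ICC .01 this is .20/√.00667 = 2.45. Two-sided unadjusted power is capped at .74, .46, .27 and .14 for ICC .005, .01, .02 and .05.

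**6. If .20 meant Cohen's f.** Then d = .40, and power is .995 at ICC 0, .82 at ICC .01 (.79 with 20% attrition) and .36 at ICC .05.

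**The case against.** The strongest reply is that .66 belongs to a test the SAP does not plan. The SAP plans a repeated-measures analysis with covariates and states neither sidedness nor a baseline correlation. With ICC 0 and a favourable choice of these, .90 can be reached: for example, one-sided with r = .7 and 20% attrition gives .94. If the ICC were truly 0, participant-level inference would be valid and give .885. On this view .90 is unsupported rather than wrong.

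Part of this stands. The .66 is not a ceiling for every analysis; it holds for a two-sided, unadjusted test on 4 df with equal clinics. But the rescues at ICC 0 need one-sided testing, a substantial baseline correlation or both, none of which is stated. At ICC .01 a two-sided test needs a correlation of .90. Nor does the shortfall depend on the 4 df once the ICC exceeds 0, as step 3 shows.

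A second reply is that the SAP has no clinic term, so the analysis as written would not lose this power. At ICC .01 an unadjusted participant-level test rejects with probability about .77 when d = .20. It also rejects about .23 of the time when there is no effect, so the .77 is not usable power at alpha .05. The missing clinic term is a separate matter, but it means the revised power sentence cannot be written independently of the analysis.

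A third reply is that Aim 1 calls the evaluation preliminary. That is a reason not to claim .90 power for a small effect.

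**Conclusion.** The concern holds: .90 is wrong as written for a design that randomises three clinics per arm. With .20 as a standardised mean difference, equal clinics and a two-sided unadjusted clinic-level test, power is at most .66 and falls to between .43 and .13 over assumed ICCs of .005 to .05, before attrition. The true ICC and attrition rate are unknown from the documents, so the exact shortfall is too. That the power sentence omits clustering does not depend on them. This must be fixed, because the sentence is the only sample-size justification in either document. The finding concerns the power figure alone.

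**What to change.** In the SAP (Statistical Design and Power Calculations) and protocol section 8 (Data Analysis), replace the power sentence with one on the clinic-randomised basis, for example:

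> With 500 participants per arm in 3 clinics per arm, a [one/two]-sided .05 clinic-level comparison on 4 df, ICC [range], attrition [x%] and baseline correlation [r, if used], power for a standardised mean difference of .20 is [range]; the effect detectable with .90 power is [range].

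The sponsor should supply or justify the ICC and attrition values and confirm the effect metric. The sentence should name the clustered analysis that the SAP finally adopts, so that the two agree; if that is not a clinic-level comparison on 4 df, the wording and figures change with it. The power paragraph should also present the trial as estimating a preliminary effect, in line with Aim 1.

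The cost is one sentence in each document and a short recalculation, and a much less favourable stated power. Enrolment and conduct do not change, and adding participants in the same six clinics would not restore .90 at any of the assumed ICCs from .005 up on the two-sided unadjusted test.

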access to COVID-19 vaccine, vaccine hesitancy). Additional measures at baseline and follow-up will be used as covariates (e.g., outreach and health communication, vaccine hesitancy or mistrust). Mean differences, both within and between treatment and control groups as well as group by treatment interaction effects will be analyzed. The targeted sample size is sufficient to detect a small effect size (.20) with power = .90 at alpha = .05 accounting for moderate participant attrition.

Descriptive Statistics. To describe the overall sample regarding demographics, structural and individual barriers, and potential covariates of intervention effects at baseline, prevalence statistics and means and standard deviation will be provided for all baseline variables; Cronbach's alpha of .70 will be required to be considered reliable. **Baseline Analyses to Detect Differences Between Treatment Groups.** Chi-square analyses and paired t-tests will be used to detect differences in demographics, knowledge of COVID-19 vaccine, access to COVID-19 vaccine, acceptance of COVID-19 vaccine and series completion, COVID-19 resource-seeking behaviors and linkage into care between intervention and control groups. Demographic variables included in these analyses will be age, gender, race/ethnicity, education, household income, marital status, and having insurance. Those variables differing across treatment groups at the $p < .20$ level will be included in subsequent adjusted outcome analyses. For the qualitative data analysis, final translated electronic transcripts will be imported into Dedoose. Analysis will be done through identification of recurrent themes following Crabtree and Miller's 5 step "interpretive process."¹⁹ First, transcripts will be read to identify common themes, codes will be developed and ~10% of data will be double coded and inter-rate reliability assessed. Coded text will be extracted and organized and read to identify emergent themes.⁶⁵ Matrices will be created to compare codes by themes (e.g., medical mistrust, discrimination, stigma, transportation, access to vaccination site, lack of insurance). Data will be utilized to refine *2VIDA!*, assess acceptability, and inform future vaccination efforts among underserved communities.

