All participants will be notified of potential risks and risk mitigation via informed digital consent for the survey (e.g., tablets) and written paper consent (for the focus groups conducted by UCSD personnel and the vaccine that will only be conducted by trained SYH registered nurses). The written paper consent process for the vaccine will be conducted by SYH staff as they will administer the vaccine, not UCSD staff. Those agreeing to participate will be escorted to a private room within the participating SYH community centers or in their cars or tents (if they come by foot) at the mini-vaccination stations and will provide informed digital consent for the survey (e.g., tablet) and complete the survey via a tablet (self-administered). Participants will have the option to email themselves the consent form or we can print it for them on site. As previously mentioned, we will set-up mini-vaccination stations in the parking of three public parks in the selected intervention sites and tent-lined lanes for eligible recipients to drive up. Participants will be inside their car and wearing a mask at all times during the consent process. Inside their car they will complete the 10-15 min. survey, receive the COVID-19 vaccine, and pull aside for a 15-minute observation period. We will also set-up additional tents with portable chairs at least 6 feet apart for participants who do not own a vehicle and want to receive the vaccine at the mini-stations. Although the mini-vaccinations will be in open public spaces (e.g., local park) because the set-up between the vaccine stations will be at least 6 feet apart, we expect this will allow for privacy for those that come by foot or do not own a vehicle. However, those participants who feel uncomfortable will be invited to the health center to complete the consent process and survey in a private room. All participants will be assigned a unique identifier to link initial survey and follow-up survey (when they

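### Baseline comparison of the arms specifies paired t-tests with no pairs defined and ignores clinic randomisation; the second fault matters more for the p < .20 covariate rule

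*SAP*

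**What the plan says.** The SAP's paragraph on baseline analyses states: "Chi-square analyses and paired t-tests will be used to detect differences in demographics, knowledge of COVID-19 vaccine". The sentence goes on to list access, acceptance and series completion, and ends: "COVID-19 resource-seeking behaviors and linkage into care between intervention and control groups". The comparison is therefore between arms. Protocol section 8 (Data Analysis) has the same text: "Chi-square analyses and paired t-tests will be used to detect differences in demographics".

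The result is then used to choose covariates: "Those variables differing across treatment groups at the $p < .20$ level will be included in subsequent adjusted outcome analyses". The SAP's demographic list is: "Demographic variables included in these analyses will be age, gender, race/ethnicity, household income, marital status, and having insurance". The protocol's list also contains education.

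On design, protocol section 10 (Recruitment) says: "Each clinic will be randomly selected and randomized evenly to either the intervention or control conditions". It also says: "Participants from both intervention (n=500) and control sites (n=500) will be recruited using reactive recruitment". The only linkage of records is within a person (protocol section 9, Human Subjects): "All participants will be assigned a unique identifier to link initial survey and follow-up survey".

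**The concern.** A paired t-test analyses differences within matched pairs. Here the two groups are separate people enrolled at separate clinics, and neither document matches participants or clinics. The one link that exists joins a person's baseline survey to the same person's follow-up survey, which cannot compare arms at baseline.

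The wording matters because the plan acts on the p-value. A variable enters the adjusted outcome analyses if it passes p < .20, so the test helps to choose the adjusted model. A prespecified step should give one answer from one dataset.

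The same sentence has a second problem. Randomisation is by clinic, three per arm, yet neither the t-tests nor the chi-square tests take account of clinic.

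**Working it through.** **Inputs from the documents.** 500 people and 3 clinics per arm; screening cut p < .20; no matching described. **Assumed.** Intraclass correlation (ICC) .01, .02 and .05, because the documents give none; 166 people per clinic (500/3, rounded down).

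**Reference figure.** The plan gives no numerical result for this step. The cut itself implies that a valid test flags 20% of variables with no true difference. In 10,000 simulated trials with independent people and 500 per arm, the independent t-test flagged 19.4%, as expected.

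**Step 1: paired test, arbitrary pairing, no clinic effect.** The squared standard error of the paired test is (s_a² + s_b² − 2·s_ab)/n. If pairing is unrelated to the values, the covariance s_ab is near zero and the standard error is nearly that of the independent test. The critical t hardly moves: 1.2833 on 499 df against 1.2824 on 998 df.

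| True difference (SD) | Paired, flagged | Independent, flagged | Decisions that differ |
|---|---|---|---|
| 0 | 19.4% | 19.4% | 0.8% |
| 0.05 | 32.7% | 32.7% | 0.9% |
| 0.10 | 61.4% | 61.5% | 0.9% |
| 0.20 | 96.8% | 96.8% | 0.1% |

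At p < .05 with no true difference the paired test flagged 4.9%.

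**Step 2: dependence on row order.** With equal variances the paired t is about the independent t divided by √(1 − r), where r is the chance correlation created by the pairing. Its SD is about 1/√499 = .045, so r lies mostly within ±.09 and t is multiplied by 1/√1.09 = .96 to 1/√.91 = 1.05. An independent p of .205 (t about 1.27) should therefore move between roughly .18 and .22. In one simulated dataset with independent p = .205, 5,000 random pairings gave a central 95% range of .185 to .224 and a full range of .166 to .238; 29% fell below .20. Further from the cut the effect vanishes. With 3,000 pairings each, the share below .20 was 0.03% at independent p = .236, 0% at .343 and 100% at .155.

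**Step 3: clinic ignored.** The design effect is DE = 1 + (166 − 1)·ICC. A test that ignores clinic flags about 2·[1 − Φ(1.2816/√DE)] of null variables at p < .20.

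| Assumed ICC | DE | 1.2816/√DE | Flagged by formula | Flagged in simulation (independent / paired) |
|---|---|---|---|---|
| .01 | 2.65 | .787 | 43% | 44% / 44% |
| .02 | 4.30 | .618 | 54% | 55% / 55% |
| .05 | 9.25 | .421 | 67% | 67% / 67% |

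Across repeated simulations the rates ran from about 42% at ICC .01 to 69% at ICC .05. A t-test on the six clinic means flagged about 20% throughout.

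**The case against.** The strongest reply is that *paired* is a slip of terminology. An analyst would run an independent t-test, software would refuse a paired test on unequal arms, and even a paired test run on arbitrary rows gives almost the same decisions. Most of this stands. With arbitrary pairing the error rate is nominal, so a reader who infers that all the screening p-values are invalid because of the word goes too far. Three other stronger readings also fail.

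- Pairing both arms after sorting on the tested variable gives extreme p-values (about 3e-35 in one simulated dataset). Nothing in either document suggests that the rows would be sorted separately for each variable.
- The error does not reach every screened variable. Gender, race/ethnicity, marital status and insurance are categorical, and income may be; the chi-square tests are untouched by it.
- No biased treatment effect has been shown. The calculations concern baseline p-values, and the documents do not allow the effect on the adjusted estimates to be worked out.

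The reply does not cure the wording, which appears in both documents within a rule that the plan acts on. Nor does it help with clinic: a silent switch to the independent t-test leaves the flag rates in step 3 unchanged.

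**Conclusion.** The point holds in a limited form. The specified test does not fit the comparison and is undefined for variables analysed by t-test, so the screen is not reproducible as written. By itself this would change a covariate decision only for a p-value close to .20, in about 1% of simulated trials or fewer.

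Ignoring clinic is the larger fault in the same step. About 42% to 69% of null variables would be flagged instead of 20%, whether the t-test is paired or independent. That range rests on the assumed ICCs of .01 to .05, three equal clinics of about 166 people per arm, and normally distributed variables. The chi-square tests ignore clinic too, but their flag rates were not calculated. The plan should be corrected; the finding does not show that the trial's conclusions would change.

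**What to change.** In both the SAP and protocol section 8:

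1. Delete the word *paired* from the baseline sentence.
2. Replace the p < .20 rule with adjustment covariates named in advance from the variables already listed, after reconciling the two lists on education. Describe balance by arm with standardised differences. Dropping baseline p-values without replacing the rule would leave covariate selection undefined.
3. If between-arm baseline tests are kept, use two-sample comparisons that allow for clinic, such as a t-test on the six clinic means or a model with a clinic random effect. Do the same for categorical variables.
4. Keep paired methods for within-person change from baseline to follow-up.

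The cost is two sentences in each document and no new data. The drawback is that a clinic-level test on six clinics has low power, which is a further reason to prespecify covariates rather than screen for them.
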